APPENDIX I: Chatbot Study Screening eQuestionnaire

3. How many weeks pregnant were you at delivery?

_____ (Open-ended question)

Study Number: OBVIO-DAN-003

Protocol V3 31AUG2018

16 Appendices

Date: _____ **Parent** Relationship to Infant: Father Mother Date of Birth: _____ (excluded if not in \geq 21 years of age) Infant Gender: Boy Girl Date of Birth: _____ (excluded if not in age group 0-6 months at time of enrollment) The following is a questionnaire to help us better understand you and your baby; this will allow us to determine if this study is right for you. Please pick the **best** answer. 1. Was your baby from a singleton pregnancy? a. Yes b. No (exclusion) 2. Was your baby born after 37 weeks of gestation? (i.e., how many weeks pregnant were you at delivery?) a. Yes b. No c. Don't Know/Not sure (exclusion)

4.	W	What type of food does your baby typically eat? (check all that apply)							
		Breastmilk	Formula	Solid-food	Other [Open-ended question]				
	(if breastmilk)								
	a.	At what approxi	mate age (in we	eeks) do you plan to	o stop feeding your baby breastmilk	?			
		[Open-ended que	estion]						
	b.	Do you know wh	en you are plan	ning on introducing	g solid food?				
		i. Yes							
		ii. No							
		(if yes) When o	lo you plan on ir	ntroducing solid foc	od? [Open-ended question]				
5.	Is your baby currently in the hospital?								
	a.	Yes (exclusion)							
	b.	No							
6.	Ar	Are you a single parent?							
	a.	Yes (exclusion)							
	b.	No							
7.	Are you proficient in the English language?								
	a.	Yes							
	b.	No (exclusion)							
8.	Do you or your baby have a significant limitation (including medical or physical concerns, etc.)								
	wh	nich may interfere	with daily study	participation for 3	0 days in a row?				
	a.	Yes (exclusion)							
	b.	No							
	c.	Don't Know/Not	Sure						

. Do you live in a household where you have reliable, easy access to the internet and					
electronic devices such as a computer, laptop, smartphone or tablet?					
a. Yes					
b. No (exclusion)					
10. Has your baby been diagnosed with a current or previous illness or medical condition					
(other than prematurity)?					
a. Yes					
b. No					
(if yes) What illness or medical condition? (open-ended response; PI to follow up)					
11. Have you been diagnosed with any of the following (please check all that apply; check "not					
applicable" if you have not been diagnosed with any of those listed below):					

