Did it ta more t minutes slee	Did it take you more than 30 minutes to get to sleep?	Please share what happened with your	Please share what kept you		Please share what happened with your baby that kept you up.	Please share what made you feel physically uncomfortable (i.e. too hot, too cold, pain, etc.)	Please share what was on your mind.	Please share what kept you awake.	[Collect open ended response]	
	Yes	baby that kept you up.	awake.			[Collect open ended response]	l response]			
S O	How come?				Was there an	Was there any other reason you may have been awoken?	ı may have be	en awoken?		
					Yes					
) (Collec	[Collect open ended response]	[əsuods:	[Return to "N	Vhat would you above]	[Return to " What would you say woke you up ?" above]		No		
				Did anythin	Did anything else affect your sleep?	ur sleep?				
				Yes						
What e	lse affecte	What else affected your sleep? [Return to "What	eturn to "Wha	rt do you think	affected your sl	do you think affected your sleep?" responses above]	love]	0 Z		
		On a scale of 1	to 4 (1 being	Very Good and	4 being Very B	On a scale of 1 to 4 (1 being Very Good and 4 being Very Bad), how would you rate your quality of sleep last night?	u rate your qu	ality of sleep	last night?	
				1	[Collect open ended response]	ded response]				
			Thanks for		. How did you f	sharing that. How did you feel when you woke up this morning?	up this morr	ing?		
								Other		
	Ē	Tired		Well-rested	sted	How would yo	λυ describe hα	ow you felt wh	How would you describe how you felt when you woke up this morning?	this morning?
							ie [Colle	[Collect open ended response]	response]	
Did you s	still feel tir	Did you still feel tired in the afternoon?		s great! Did you fee afternoon?	That's great! Did you feel tired in the afternoon?	a l	Did you f	Did you feel tired in the afternoon?	e afternoon?	
				[All c	questions lead t	[All questions lead to these responses]				
				Yes					No	

			I'm glad to hear that! Would you like	some additional information on improving sleep quality overall?				No	
ır way?		ua.	Ç	2		I'm sorry to hear that. Would you find it helpful if we shared some additional information on improving sleep quality overall?			with me today!
Did you take a nap or manage being tired in any other way?		ou take? Other [Collect open ended response]			ON N	I'm sorry to hear that. Would me additional information o		proving sleep and sleep althy/510/sleep	Thanks for chatting with me today!

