Did you take a nap or m	Medication	What medication did you take?	[Collect open ended response]	Did this help?			Yes	Great! This link has a lot of information about improving sleep and sleep quality: http://www.healthhub.sg/live-healthy/510/sleep	
		Nap Caffeine			Yes	I'm glad to hear that you're feeling less tired! Would you like some additional information on improving sleep quality overall?		Great! This link has a lot quality: http://w	

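### The Sleep Script prompts for only one way of managing tiredness per session, so method-specific counts by preterm/full-term group may be too low

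*SAP*

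**What the plan says.** SAP Appendix II (Sleep Script) asks parents who report afternoon tiredness "Did you take a nap or manage being tired in any other way". The branches are Nap, Caffeine, Medication (with its own follow-up, "What medication did you take"), a free-text Other, and No. The methods lead to one question, in the singular, on whether this helped. The offer of sleep information and the close come next. The layout shows no prompt for a second method, no instruction to return to the list, and no statement that one or several answers are allowed.

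Earlier in the same script, several answers are sought explicitly. Causes of waking are followed by "Was there any other reason you may have been awoken", and a yes returns to the list of causes. Causes of poor sleep are followed by "Did anything else affect your sleep", and a yes leads to "What else affected your sleep" and back to the list. The screening questionnaire (Protocol Appendix I) marks its multi-answer items "check all that apply".

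SAP 8.7.2 plans bar charts that enumerate categories and theme frequencies for open-ended script answers, all stratified by preterm versus full-term. SAP 8.4 leaves the secondary endpoint variables to be agreed later. No endpoint is named for nap, caffeine or medication use.

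**The concern.** Napping and drinking coffee on the same tired day is not a contradiction, so the natural answer to this item is a set. If one branch is followed per session, the methods compete for one slot, and more use of one method lowers the recorded count of another. Two groups that nap equally often could then show different nap counts only because their caffeine use differs. The secondary objective is the preterm versus full-term comparison, and the script outputs are stratified that way.

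The helpfulness answer has a related problem. When two methods were used, one yes or no cannot be assigned to either of them.

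**Working it through.** **1. Script flow, side by side (SAP Appendix II).**

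| Item | Repeat prompt | Return to list |
|---|---|---|
| Causes of waking | yes | yes |
| Causes of poor sleep | yes | yes |
| Ways of managing tiredness | none shown | none shown |

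The sleep flow is printed again under the Appendix III heading, and the tiredness block there shows no return instruction either. The return instructions for the causes survive in both copies, so lost text is an unlikely explanation for the gap.

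**2. Inputs for size.** The plan gives no figure on this point, so there is nothing to reproduce. It gives 20 parents per group (SAP Section 6) and at most 3 × 4 = 12 sessions each (SAP 7.1), which is at most 240 sessions per group. The number of sessions with afternoon tiredness is not given. The following are assumptions for illustration only:
- nap use n = 40% of tired sessions in both groups
- caffeine use c = 60% in one group and 90% in the other
- the two used independently
- one method recorded per session
- the same naming habit in both groups

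**3. Formulas.** Dual use is b = n × c. Let p be the share of dual-use sessions recorded as caffeine.
- Recorded nap = n − p × b
- Recorded caffeine = c − (1 − p) × b
- Any use = n + c − b, which does not depend on p

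Dual use is b = 0.40 × 0.60 = 0.24 and 0.40 × 0.90 = 0.36.

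| Naming rule | Recorded nap | Nap difference (true 0) | Recorded caffeine | Caffeine difference (true 30) |
|---|---|---|---|---|
| Nap always named (p = 0) | 40% v 40% | 0 | 36% v 54% | 18 |
| Either at random (p = 0.5) | 28% v 22% | 6 | 48% v 72% | 24 |
| Caffeine always named (p = 1) | 16% v 4% | 12 | 60% v 90% | 30 |

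In general, the false nap difference is p × (0.36 − 0.24) = 0.12p, and the recorded caffeine difference is 0.30 − 0.12 × (1 − p). Any use is 0.40 + 0.60 − 0.24 = 76% and 0.40 + 0.90 − 0.36 = 94%, whichever method is named.

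**4. Method mentions lost.** If a share m of method-using sessions involve exactly two methods and one is recorded, the share of mentions lost is m/(1 + m). This is 9.1% at m = 10%, 16.7% at 20%, 23.1% at 30% and 33.3% at 50%. At m = 0 nothing is lost. The value of m is not in the documents.

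**The case against.** The strongest objection is that single choice is inferred. A reader might conclude from the layout that the chatbot accepts one answer only, but neither document says so. The absence of a multi-select label proves little, because the comparison is with a screening form and not a dialogue. The script table is also badly broken in the text available.

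Other routes may capture a second method. The tool is conversational and its transcripts are reviewed (SAP 7.5), a transcript is kept for each interaction (SAP 7.2), free text is coded in RQDA (SAP 8.4.1), and Other is open-ended. A parent who types both methods could be coded to both. This stands, and it limits how certain the loss is. It does not remove the gap: the script never asks for a second method, so capture would depend on what each parent volunteers.

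The consequence is also bounded. No named endpoint rests on this item, the figure titles are in a TLF shell outside these documents, and the study is a descriptive pilot with no hypothesis test specified. That stands and keeps the point modest.

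Finally, a reader might infer that medication is the method most easily hidden behind another. The documents give no frequency or order of mention for medication, and it has its own follow-up, so that inference is unsupported.

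**Conclusion.** The point holds in a limited form. The script prompts for one way of managing tiredness and loops for causes but not for methods. Followed as drawn, it may under-count individual methods by group and leaves the helpfulness answer unattributable when two methods were used.

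Two stronger readings are not supported:
- **Use as a whole is under-counted.** It is not: the share using at least one method is the same whichever method is recorded.
- **A false group difference in naps is bound to appear.** On the assumptions above it runs from 0 to 12 points. Zero is a plausible case, because the nap is the only method named in the question. In that case the distortion moves to caffeine, where a true 30-point difference is recorded as 18.

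These sizes rest on assumed use rates, independence, one recorded method per session and the same naming habit in both groups. If no parent uses two methods on the same day, method counts are unaffected. The true size is unknown.

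**What to change.** Make the item multi-select, or reuse the loop that the script already has for causes. Ask whether it helped once for each method named. Report each method as its own yes/no per tired day, by group.

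If sessions have already been collected, code every method mentioned in the transcripts as its own yes/no. Label the output as one prompted method per session, so that readers do not take the counts as complete.

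The cost is one script edit, or one coding rule and a footnote. For parents, the loop version adds about four prompts when two methods were used (anything else, which method, whether it helped, anything else) and one prompt when a single method was used. Multi-select adds about one helpfulness question per extra method. Interaction length is itself rated in the usability questionnaire (question 8), which favours multi-select if the platform allows it.

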Appendix III: Stress Script

				How did you sl	How did you sleep last night?				
		Good				Not	Not well		
Thanks for sharing that. How many total hours of night?	g that. How ma	any total hour night?	s of sleep did you get last	ou get last	Thanks for sh	Thanks for sharing that. How many total hours of sleep did you get last night?	any total hours night?	of sleep did y	ou get last
[Collect open ended numerical response and filter	ed numerical re	esponse and fil	lter into below categories]	ategories]	[Collect open	[Collect open ended numerical response and filter into below categories]	onse and filte	er into below c	:ategories]
<7 hours	7 h	≥7 hours	I don't know	know	<7 hours	≥7 hours		I don't know	now
7		7	That's ok, I only need an estimate.	nly need an ate.		That is a good amount of		That's ok, I only need an estimate.	ly need an ite.
r m glad you still reel well-rested. Did anything affect your		I nat Is a good amount of sleep! Did anything bother you	[Collect open ended numerical response]	en ended en ended	What do you think affected	sleep. Why do you feel like you didn't sleep well?		llect open ended response]	[Collect open ended numerical response]
sleep?	about yo	about your sleep?	Please share what may have affected your sleep last night.	what may I your sleep ght.	your sleep	Did anything bother you about your sleep?		Please share what may have iffected your sleep last night.	Please share what may have affected your sleep last night.
			[All q	questions lead	[All questions lead to these responses]	I			
			I woke u	I woke up during the night.	ight.				
I went t	I went to bed too late.		Sorry to hear how often you	Sorry to hear that, do you remember how often you woke up? [Collect open ended response]	emember ollect open	I woke up too early.		Other	Nothing affected my
Sorry to hear that, what in particular kept you awake?	what in particu awake?	lar kept you		What wo	What would you say woke you up?	you up?	Wh	What do you	Skip to question
I couldn't get to sleep	My baby	Other	I had to go to the bathroom	My baby	Physical discomfort	I had a lot on my Ot mind	Other yo	feel affected your sleep?	below]

Did it ta more t minutes slee	Did it take you more than 30 minutes to get to sleep?	Please share what happened with your	Please share what kept you		Please share what happened with your baby that kept you up.	Please share what made you feel physically uncomfortable (i.e. too hot, too cold, pain, etc.)	Please share what was on your mind.	Please share what kept you awake.	[Collect open ended response]	
	Yes	baby that kept you up.	awake.			[Collect open ended response]	l response]			
S O	How come?				Was there an	Was there any other reason you may have been awoken?	ı may have be	en awoken?		
					Yes					
) (Collec	[Collect open ended response]	[əsuods:	[Return to "N	Vhat would you above]	[Return to " What would you say woke you up ?" above]		No		
				Did anythin	Did anything else affect your sleep?	ur sleep?				
				Yes						
What e	lse affecte	What else affected your sleep? [Return to "What	eturn to "Wha	rt do you think	affected your sl	do you think affected your sleep?" responses above]	love]	0 Z		
		On a scale of 1	to 4 (1 being	Very Good and	4 being Very B	On a scale of 1 to 4 (1 being Very Good and 4 being Very Bad), how would you rate your quality of sleep last night?	u rate your qu	ality of sleep	last night?	
				1	[Collect open ended response]	ded response]				
			Thanks for		. How did you f	sharing that. How did you feel when you woke up this morning?	up this morr	ing?		
								Other		
	Ē	Tired		Well-rested	sted	How would yo	λυ describe hα	ow you felt wh	How would you describe how you felt when you woke up this morning?	this morning?
							ie [Colle	[Collect open ended response]	response]	
Did you s	still feel tir	Did you still feel tired in the afternoon?		s great! Did you fee afternoon?	That's great! Did you feel tired in the afternoon?	a l	Did you f	Did you feel tired in the afternoon?	e afternoon?	
				[All c	questions lead t	[All questions lead to these responses]				
				Yes					No	

			I'm glad to hear that! Would you like	some additional information on improving sleep quality overall?				ON.	
r way?		u:	Ç			I'm sorry to hear that. Would you find it helpful if we shared some additional information on improving sleep quality overall?			with me today!
Did you take a nap or manage being tired in any other way?		(e? Other [Collect open ended response]			No	rry to hear that. Would Iditional information or		Great! This link has a lot of information about improving sleep and sleep quality: http://www.healthhub.sg/live-healthy/510/sleep	Thanks for chatting with me today!
or manage bei	ation did vou take	n did you tak	ded respons	þ			bout improvi		
Did you take a nap	Medication	What medication did you take?	[Collect open ended response]	Did this help?		I'm glad to hear that you're feeling less tired! Would you like some additional information on improving sleep quality overall?	Yes	This link has a lot of information about improving sleep an quality: http://www.healthhub.sg/live-healthy/510/sleep	
		Caffeine			Yes	lad to hear that you're feeling less t ild you like some additional informa on improving sleep quality overall?		link has a lot lity: http://w	
		Nap				I'm glad to h Would you l on impi		Great! This	

Appendix IV: Nutrition Script

Thanks for sharing that. How many total hours of sleep did you get last night? Collect open ended numerical response and filter into below categories Collect open ended numerical response and filter into below categories Collect open ended numerical response That is a good well-rested. Did amount of sleep! Did amount of sleep! Did numerical response Sleep? Please share what may layen?
hours of sleegand filter into base [Coll and please have af ha
hours of sleep and filter into b That's a coll id num Please have af
That's (Coll have af
Please have af
I woke up during the night.
Sorry to hear that, do you remember how often you woke up? [Collect open ended response]
Sorry to hear that, what in particular kept you awake?
I had to go to the bathroom

Did it more minute sl.	Did it take you more than 30 minutes to get to sleep?	Please share what happened with your	Please share what kept you		Please share what happened with your baby that	Please share what made you feel physically uncomfortable (i.e. too hot, too cold, pain, etc.)	Please share what was on your mind.	Please share what kept you awake.	[Collect open ended response]	
	Yes	baby that kept you up.	awake.			[Collect open ended response]	l response]			
o Z	How come?				Was there an	Was there any other reason you may have been awoken?	may have be	en awoken?		
					Yes					
	Sollec	[Collect open ended response]	:sponse]	[Return to "	Nhat would you above]	[Return to " What would you say woke you up ?" above]		No		
				Did anythin	Did anything else affect your sleep?	ur sleep?				
				Yes						
What	else affecte	d your sleep? [R	eturn to "Wha	xt do you think	affected your sl	What else affected your sleep? [Return to "What do you think affected your sleep?" responses above]	lovel	No		
		On a scale of 1	to 4 (1 being	Very Good and	14 being Very B	On a scale of 1 to 4 (1 being Very Good and 4 being Very Bad), how would you rate your quality of sleep last night?	ו rate your קנ	uality of sleep	last night?	
					[Collect open ended response]	ded response]				
			Thanks for		t. How did you f	sharing that. How did you feel when you woke up this morning?	up this morr	ing?		
								Other		
	Ē	Tired		Well-rested	sted	How would yo	n describe hα	ow you felt wh	How would you describe how you felt when you woke up this morning?	this morning?
							ie [Colle	[Collect open ended response]	response]	
